### 3) Sensitivity analysis

- a. No sensitivity analyses will be done beyond those described above.

### 4) Subgroup analysis

- a. Additional models and statistical interactions (i.e., product terms) will be performed to identify characteristics of individuals who most benefitted from the intervention, such as East Bay versus San Francisco, sex, race/ethnicity, food insecurity, poor T2DM control ( $A1c \geq 9$ ), and insulin use.

### 5) Missing data

The study will use several strategies to account for and address missing data. Missing data will be categorized into missed individual questions and missed visits.

- a. Missed individual questions: If needed, multiple imputation will be used to address incomplete data under the weak assumption that incomplete data arise from a conditionally missing-at-random mechanism (MAR) rather than the missing-completely-at-random process assumed by ad hoc methods such as listwise deletion. Auxiliary variables will be included to help meet the MAR assumption and sensitivity analyses will be conducted with weighted multiple imputation to assess the MAR assumption. Information on percent of questions missing and imputed will be reported for each variable as appropriate in study manuscripts.
- b. Missed visits: When a participant misses a visit, this will be noted in the study register, and no data will be imputed for this participant for that visit.

### 6) Additional analyses

- a) **Durability of health benefits:** To assess whether any improvements in primary, secondary, and intermediate outcomes were sustained in the intervention arm, researchers will estimate effects of the intervention on outcomes measured at 12 months. We will specifically assess the durability of HbA1c values and of the food security score from six months to twelve months in the intervention arm. For the intervention arm only, mixed models specifying two visit fixed effects will be used, one for differences between baseline and six months and one specifying differences between six and 12 months. The random effect will be individuals.

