Control condition. Control participants will receive the standard of care as offered by clinical partners to all T2DM participants, including referral to nutritional counseling, T2DM support groups, and participation to local diabetes self-management programs. Control participants are also often provided referral information for locally available food support services in the region that provide diabetes-appropriate foods. After 6-months, the control arm will have the opportunity to receive diabetes-tailored food support from POH along with nutritional counseling, regardless of whether they meet regular POH eligibility criteria. The services that the control group will receive after the six-month period will be similar to what the intervention group receives during the intensive CHEFS-DM intervention - 6-months of food sufficient to meet 67% of their daily requirements, video recordings of the 4 CHEFS- DM intervention nutrition education classes and access to a POH RD at their request.

Given that POH could not easily absorb a large number of additional new clients in a relatively short time frame, the wait time is also in line with programmatic considerations.

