## 5) Data collection

Follow-up will be broken up into two phases. From baseline to six months, the CHEFS-DM intervention will be implemented, and researchers will follow both intervention and control arm participants (n=281 (actual)). After the end of the six-month follow-up, the intervention arm will transition to receiving standard POH services (comprising 33% to 67% of daily energy requirements depending on health status), and will be followed for an additional six months, to assess the extent to which any health benefits are sustained at 12 months (n=156). Hence, control arm will be followed for 6 months and participate in two assessments, and the intervention arm will be followed for 12 months and participate in three assessments.

At baseline and 6 months for all participants and at 12 months for intervention arm, the following data will be collected:

a) Structured interviews (baseline, 6 and 12 months). Trained UCSF research assistants (RAs), including Spanish/English bilingual RAs, will administer the structured interview either in person or over the phone and/or zoom, depending on public health protocols and acceptability of in-person visits to participants due to COVID-19. When visits are conducted in-person, interviews will take place in private offices at POH, in a private room at a partner clinic (if available), in a private location at a community space (e.g. library, community center), or at a private location of the participants choosing (e. g. home visit).

The content of the interviews will cover:

- Socio-demographic information.
- Food insecurity and diet quality
- Physical activity
- Mental health (e.g., depressive symptoms, diabetes distress and social support, self- efficacy for following T2DM recommendations).
- Adherence to T2DM medications.
- Health care utilization (e.g., missed clinic visits, acute care use (hospitalizations and emergency department visits)).
- Health-related quality of life.
- Medication inventory (for cardiometabolic conditions only).
- Diabetes co-morbidities (e.g. nephropathy, retinopathy).
- Economic information (e.g. economic impacts of COVID-19, household expenditures on food).

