- d) Blood draws (baseline, 6, and 12 months): Participants will undergo a blood draw (testing a lipid panel, and HemoglobinA1c) at one of 28 Quest Diagnostics labs in San Francisco or Alameda counties Phlebotomy will be performed using universal precautions. Date and time of phlebotomy, and specimen number will be recorded in a participant log. Specimens will be aliquoted and stored at -70°C using standard universal precautions. Data will be received from Quest Diagnostics in the form of a spreadsheet which can be easily merged with other study data by participant ID or will be accessed by UCSF staff using the secure Quest Diagnostics HIPPA-compliant online portal. At baseline and six months, all participants will undergo the blood draw; at twelve months, the blood draw will be implemented in the intervention arm only.
- e) 24-hour Dietary Recall (baseline and 6 months). Dietary intake will be assessed via 24-hour dietary recalls by UCSF RA trained by registered dietitians using the National Cancer Institute's Automated Self- Administered 24-hour Dietary Recall (ASA24). Participants will complete two unannounced recalls (one weekday and one weekend day) during a one-week period. In total, participants will complete four recalls: 2 at baseline and 2 at 6-month follow- up. RA's will inform the participant of which week the calls will be attempted. Previous work has indicated that lower income or older adults may need additional assistance with completing the ASA24, therefore the questions will be administered over the phone or in person (if COVID permits), using strategies to ensure the collection of dietary data is accurate and does not burden the participant. The 24-hour dietary recall will be conducted at baseline and six-month follow up.
- f) Medical record review (baseline, 6, and 12 months). Medical records will be used

during recruitment to confirm T2DM diagnosis, to confirm participant HbA1c, preferentially greater than or equal to 6.5%, and to determine whether a patient has controlled or uncontrolled T2DM using latest HbA1C test result. Medical record review is also being used to collect follow-up HbA1c data if completing a blood draw is not possible during follow-up, if medical record A1c is available within the assessment time frame, and with the consent of the participant.

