### 2) Eligibility – summary of eligibility

criteria Inclusion Criteria:

1. Confirmed diagnosis of T2DM confirmed by medical or laboratory records. For T2DM, the criteria (from the American Diabetes Association) are glycated hemoglobin (HbA1c)  $\geq 6.5\%$ , or fasting plasma glucose of  $\geq 126$ , or a 2-hour plasma glucose level of 200 or higher during a 75 g oral glucose tolerance test, or a random plasma glucose of 200 or higher in patients with symptoms of hyperglycemia.
2. Age  $\geq 18$  years.
3. Screening positive for food insecurity (at least one positive question) in the previous 6 months assessed using the 6-item version of the US Household Food Security Survey Module (US Department of Agriculture) or has household income  $<200\%$  of the federal poverty level.
4. English or Spanish language fluency.
5. Adequate cognitive and hearing capacity to consent and complete study measures.
6. Reside in Alameda County or San Francisco County.

Exclusion Criteria:

1. Type-1 diabetes mellitus
2. Individuals with disorders known to affect the accuracy of the HbA1c measure (e.g., end stage renal disease and individuals with known hemoglobinopathies).
3. Inability to attend the educational workshops.
4. Inability to schedule baseline assessments and/or blood draw after repeated requests.
5. Pregnant individuals, or individuals planning to get pregnant within 6 months, or are lactating, or are postpartum less than 6 months.
6. Current POH clients, past POH clients who stopped services less than 6 months prior, or past or present participants in other POH medically tailored meals studies.
7. Does not have access to food storage, including a refrigerator and freezer to safely keep food.
8. Does not have access to facilities to reheat and prepare meals using

Project Open Hand food.

9. Anticipates moving out of study area of Alameda and San Francisco Counties in the next 6 months.
10. Receives more than 1 meal per day from a free food support resource or agency.
11. Allergic to or will not eat eggs, soy, wheat, nuts, seeds or seed oils, or other foods commonly included among ingredients in POH meals.
12. Allergic to dairy products, or unable to tolerate any dairy products including milk, yogurt, and cheese.
13. Individual does not eat any or all of POH's meat meal options and will not eat the vegetarian POH meal option.

3) **Recruitment** – A CONSORT flow diagram will be used to summarize the number of participants who were:

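### The durability analysis promises a 12-month intervention effect, but its single-arm model gives only within-arm change and is not tied to the randomised 6-month effect

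*Combined protocol and SAP*

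**What the plan says.** Section 6, Additional analyses, a) Durability of health benefits, opens in within-arm terms: "To assess whether any improvements in primary, secondary, and intermediate outcomes were sustained in the intervention arm". It then states the target as an effect: "researchers will estimate effects of the intervention on outcomes measured at 12 months". It singles out HbA1c and the food security score over months 6 to 12. The model is given as "For the intervention arm only, mixed models specifying two visit fixed effects will be used", with one effect for each six-month step and a random effect for the individual. The section does not define what counts as sustained, does not refer to the between-arm result, and states no assumption about controls after month 6.

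There is no control at 12 months by design. Section 3, Data collection: "control arm will be followed for 6 months and participate in two assessments". Section 3, Intervention description, adds: "After 6-months, the control arm will have the opportunity to receive diabetes-tailored food support from POH". Control data at baseline and 6 months do exist. They feed the Aim 1 analysis of covariance and the secondary arm-by-visit mixed model (Section 6, Analysis methods), in line with the between-arm comparison set out in Section 3, Framework. Section 6, Sensitivity analysis, adds nothing further.

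**The concern.** A pre-post change in one arm is the intervention effect plus everything else that moved the outcome. Three features of the plan make a non-zero background change plausible.

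- Controls receive active usual care, including "referral to nutritional counseling, T2DM support groups, and participation to local diabetes self-management programs".
- Entry is partly selected on the outcomes. One route is "Screening positive for food insecurity (at least one positive question) in the previous 6 months", and HbA1c of at least 6.5% is preferred.
- Visits six months apart fall in opposite seasons.

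The trial measures the controls' 0-to-6-month change for both named durability outcomes, but the durability model leaves it out. At stake is Aim 3b, on whether benefits last. Background change could be presented as a retained intervention effect. If controls worsen, a real effect could show little within-arm improvement. The primary 6-month comparison is not affected.

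**Working it through.** **Inputs from the plan.** SD of HbA1c change 1.3937, difference 0.5, one-sided alpha 0.05, power 80%, attrition 20% (Section 3, Sample size); 156 intervention and 125 control participants (Section 7). Evaluable numbers after 20% attrition: 156 × 0.8 ≈ 125 and 125 × 0.8 = 100.

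**Assumptions, not in the documents.** The controls' 0-to-6-month change c, varied from 0 to an improvement of 0.5 and also taken as a worsening. The same SD of change for the 0–6, 6–12 and 0–12 month intervals.

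**Reproducing the plan's figure.** n per arm = 2 × (1.645 + 0.842)² × 1.3937² / 0.5² ≈ 96.1, so 97 per arm and 194 in total, against the stated 98 and 196. Then 196/0.8 = 245, as stated. The durability analysis has no sample size of its own, so this only confirms the SD used below.

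**What each coefficient contains.** Negative values are improvement; E6 and E12 are the intervention effects at 6 and 12 months.

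- 0–6 step = c + E6
- 6–12 step = (E12 − E6) + any background change after month 6

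Within-arm SE = 1.3937/√125 = 0.125; 95% half-width 1.96 × 0.125 = 0.244.

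**Effect of −0.5 wholly lost, background persists, c = −0.3.**

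- 0–6 step: −0.3 − 0.5 = −0.80
- 6–12 step: +0.50, CI about 0.26 to 0.74, so the loss is visible
- Implied 0–12 change: −0.30, CI −0.54 to −0.06
- Share of the 6-month improvement still present: 0.3/0.8 = 38%, with none of the effect left

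The share for other control improvements is c/(c + 0.5), taking c as the size of the improvement:

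| Assumed control improvement | 0 | 0.1 | 0.2 | 0.3 | 0.4 | 0.5 |
|---|---|---|---|---|---|---|
| Share remaining after full loss | 0% | 17% | 29% | 38% | 44% | 50% |

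**No intervention effect at all.** In 4,000 simulated trials with 125 evaluable in the arm, the two planned steps gave a 0–6 CI below zero together with a 6–12 CI including zero in about 2% of trials with no background change, and in about 35%, 64% and 93% with background improvement of 0.2, 0.3 and 0.5. Taken alone, that pattern looks like a sustained benefit.

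**Controls worsen by 0.3.** A true −0.5 effect gives a 0–6 step of +0.3 − 0.5 = −0.20, CI −0.44 to 0.04.

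**Background that reverses after month 6, for example a seasonal −0.3.** With the effect fully kept, the arm goes from −0.80 to −0.50, so the 6–12 step is +0.30 although nothing was lost. The uncontrolled second step can therefore mislead too.

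**Control-referenced sum.** Randomised 6-month difference + within-arm 6–12 change = (intervention 12 − 0) − (control 6 − 0). SE = 1.3937 × √(1/125 + 1/100) = 0.187; half-width 0.37.

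- Background persists: 0.00 if the effect is lost (−0.5 + 0.5), −0.50 if kept.
- Background of −0.3 reverses: −0.5 + 0.3 = −0.20 if kept; −0.5 + 0.8 = +0.30 if lost.

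With g for control drift after month 6, the remaining effect is the sum minus g. Full reversal is g = +0.3, giving −0.20 − 0.3 = −0.50 and +0.30 − 0.3 = 0.

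**The case against.** The strongest reply is that the plan does not set the criterion a reader might infer, namely that a 12-month value better than baseline would count as sustained. That stands. The section names durability over months 6 to 12, gives that interval its own coefficient, and does not list 12 months against baseline as a contrast. Under full loss the coefficient would be +0.50 and clearly away from zero. The 38% figure is therefore not a planned output. It describes what the within-arm trajectory would contain.

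It can also be said that Aim 3b asks about improvements in the intervention arm, and that the existence of a 6-month effect is judged in the Aim 1 analyses with control data. Both are true, and a reader could set the results side by side. The plan does not require this, however, and the durability section itself claims intervention effects.

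Regression to the mean should not be treated as established. HbA1c is screened from medical records while the outcome baseline is a separate study blood draw, so part of any regression occurs before baseline. The 6.5% level is only a preference, and food insecurity is one of two alternative entry routes, the other being income. Season is likewise only a possible contributor.

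Finally, a reader might infer that the trial already holds the data to recover the 12-month effect, so that the control-referenced sum should decide the matter. The documents do not support this. Controls stop at 6 months and are then offered food support, so the sum rests on an untestable assumption and, as shown above, misleads if the background change reverses.

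**Conclusion.** The concern holds as a mismatch between the stated target and the model. The single-arm model estimates within-arm change, its first step mixes effect and background, its second step is uncontrolled, and nothing ties a durability claim to the randomised 6-month effect. The model can show a loss after month 6; it cannot show that there was an intervention effect to lose or keep.

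The size is conditional. The first-step contamination is nil if controls do not change. It is 38% of the 6-month improvement under an assumed persisting control improvement of 0.3 with a 0.5 effect, and 17% to 50% for control improvements of 0.1 to 0.5. These control changes, and the common SD across intervals, are assumptions. The control data at 6 months will supply the first. No analysis of this design fully identifies a 12-month effect.

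**What to change.** 1. In the durability section, state the target as within-arm change to 12 months instead of an intervention effect at 12 months.
2. Make any statement that a benefit was sustained conditional on the randomised between-arm effect at 6 months. Report that effect with its 95% CI beside the within-arm 6-to-12-month change with its 95% CI.
3. As a supplementary estimate, fit both arms jointly (control at 0 and 6 months; intervention at 0, 6 and 12 months) and report the sum of those two quantities with its 95% CI. State that it assumes controls would have stayed at their 6-month level, and show a range for control drift that includes full reversal. Do not make the sum the sole criterion for a sustained benefit.

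The cost is SAP wording, one joint model and one linear combination from data already in the collection plan, with no new visits. The supplementary estimate is less precise (SE about 0.19 against 0.125 for HbA1c with 125 and 100 evaluable) and carries an assumption about controls after month 6 that cannot be tested.

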### 7) Harms

Research will be conducted according to Good Clinical Practice guidelines, the

U.S. Code of Federal Regulations (CFR) Title 21 CFR (Part 50 – Protection of Human Subjects and Part 56 – Institutional Review Boards), and the Declaration of Helsinki.

- a) Data safety:** Participant confidentiality will be prioritized following strict guidelines on privacy. For the proposed study, all data will be collected in private and be handled as confidentially as possible within the law. For interviews, anthropometric and blood pressure assessments, 24-hour dietary recall, and medical record and laboratory data collected as part of the study, participants will be assigned a unique study identification number, and the participant's name or other public identifiers (e.g., phone number, address) will not be included with any data. All consent and other material with personal identifiers (e.g., recruitment and follow-up tracking documents) will be kept separately from all data sources. The project manager will keep consent materials in a locked cabinet in a locked office and/or in a password protected file on an encrypted computer. Research assistants and support staff will be trained on procedures for maintaining privacy and will sign a pledge of confidentiality. All electronic records (computer, online, audio-recorder) will be password protected and encrypted to prohibit illicit access. When these procedures are followed, it is highly unlikely that any information revealed by participants during the study will be disclosed to the analyst or anyone outside the research team.
- b) Adverse events.** The co-PIs will report all serious events and problems having to do with participant safety to UCSF's Human Research Protection Program within ten working days. All serious adverse events and events associated with the study participation will be reported in writing. Drs. [name] and [name] will annually provide a discussion of any problems noticed during the previous year of the study to the UCSF Human Research Protection Program during the annual review. Participants will be provided with information on how to contact the study staff to report serious adverse events and adverse events associated with study participation. Field staff will be trained to collect information about serious adverse events that will be sent to the study principal investigators. All serious adverse events related to the study, will be reported by arm. No formal statistical analysis will be done.

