## Section 6: Analysis

### 1) **Outcome definitions**

Primary Outcome Measures:

1. Hemoglobin A1c. At baseline and six months, all participants will undergo the blood draw; at twelve months, the blood draw will be implemented in the intervention arm only. The change on HbA1c from baseline to six months by study arm will be reported.
2. Food security. Food insecurity will be measured with the adult version of the USDA Household Food Security Survey Module (HFSSM), validated in many populations. The score ranges from 0 to 10 . Higher scores indicates higher severity of food insecurity. The change in the food insecurity scores from baseline to six months by study arms will be reported.

Secondary Outcome Measures:

1. Glucose control. The change in the proportion of participants with glucose control, defined as HbA1c <9%, from baseline to six months by study arms will be reported.
2. Low food security. Food security as a binary response will be assessed, identifying a participant having low or very low food security or food security (food security or marginal food secure) by study arm.

3. Systolic and diastolic blood pressure. Changes in the average of three repeated measurements of systolic and diastolic blood pressure (mmHg) from baseline to six months by study arm will be reported.
4. Medication adherence. A Single-Item Rating Visual Analogue Scale (range 0-100) for medication adherence will estimate the percentage of medications taken in the past month and is reliable and valid, including in low-literacy populations. The change in medication adherence (percentage points) from baseline to six months between intervention and control arms will be reported.
5. Acute care utilization. Information on acute care utilization (emergency department and urgent care) by self-report and/or medical record review will be collected. The proportion of participants that used acute health care from baseline to six months by study arm will be reported.
6. Hospitalization. Information on hospital admissions will be collected by self-report and/or medical record review. The proportion of participants with at least one event of hospitalization will be reported by study arm.
7. Missed outpatient visits. Information on missed outpatient visits will be collected by self-report and/or medical record review. The proportion of participants that missed at least one outpatient visits from baseline to six months will be reported.

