## Section 7: Changes from previous Protocol/SAP version

Protocol/SAP Version 2 changes: This version of the Protocol/SAP includes several changes to the trial approved by NIH (January 2024) and the UCSF IRB since the initial Protocol/SAP (Version 1) was registered.

- Sample size change: Our original proposed sample size was n=440 (n=220 in each arm). Given challenges with recruitment during and after the COVID pandemic, we re-calculated the sample size using updated power calculations with early data from the trial for the standard deviation in HbA1c and assuming 80% power for a one-sided test at alpha of 0.05 rather than 90%. Our new minimum sample size was calculated as n=246 (n=123 in each arm). As recruitment has ended as of June 2024, the final actual sample size is n=281 (n=156 in intervention and n=125 in control).
- Reduced measures: To reduce participant and staff burden, we reduced the number of measures and procedures. The changes included:
  - Removed fasting requirement and therefore fasting glucose and fasting lipids (still measuring non-fasting lipids)
  - Removed the following scales or measures at all time points:
    - Anxiety
    - Physical activity
    - Social support
    - Select items on economic status
    - Waist and hip circumference
  - Reduced the following scales or measures at all time points:
    - Reduced food security scale to retain adult items only
  - Removed the following measures at 12 months only
    - Weight
    - Blood pressure
- Medical record review: Allowed using an A1c from the medical record *if* blood draw was not possible at follow-up, if medical record A1c is available within the assessment time frame, and with the consent of the participant. We are not collecting medical record information on healthcare utilization and medications as this was not possible given the final sample was recruited from across the community and a wide array of healthcare settings/systems with variable payers.
- Statistical model: Our primary analysis will employ analysis of covariance rather than mixed effects (mixed effects will be employed as a secondary analysis).

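### The only planned by-arm harms report is limited to study-related SAEs, so it cannot serve as a between-arm safety comparison

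*Combined protocol and SAP*

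**What the plan says.** Section 6, Harms, b) Adverse events makes three separate statements about SAEs.

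- Collection: "Field staff will be trained to collect information about serious adverse events that will be sent to the study principal investigators".
- Written reporting: "All serious adverse events and events associated with the study participation will be reported in writing".
- Presentation by arm: "All serious adverse events related to the study, will be reported by arm", followed by "No formal statistical analysis will be done".

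The collection sentence has no relatedness condition. The written-reporting sentence is most naturally read as covering all SAEs plus any event associated with participation. The same paragraph draws that distinction when it describes what participants are told to report. Only the by-arm sentence is limited to study-related SAEs. No other section commits to a by-arm summary of all SAEs or of deaths. Nothing says who judges relatedness, by what criteria, or whether that person knows the arm.

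Other sections bear on how the sentence works in practice:

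- Section 3, Intervention description: "Control participants will receive the standard of care as offered by clinical partners to all T2DM participants". Food support from the study partner is offered to controls only after six months.
- Section 3, Data collection: controls are followed for 6 months and the intervention arm for 12.
- Section 6, Outcome definitions, has two secondary outcomes with no relatedness condition. For hospitalization: "The proportion of participants with at least one event of hospitalization will be reported by study arm". For emergency department and urgent care use: "The proportion of participants that used acute health care from baseline to six months by study arm will be reported".
- Section 7, on medical record review: "We are not collecting medical record information on healthcare utilization and medications".

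**The concern.** In a randomised trial, comparing all serious events by arm needs no judgement about cause, because the control arm supplies the background rate. A relatedness filter removes that background.

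In months 0 to 6 the intervention arm receives food, counselling and classes. The only study exposure of controls is to procedures such as interviews and blood draws. An SAE in a control participant therefore has few routes to being called related, while one in an intervention participant has many. Whoever makes the call probably knows the arm: the nature of the intervention makes masking unlikely, and none is described.

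Two misreadings follow. A handful of related events in one arm and none in the other can look like excess harm when there is none. A real excess or reduction among events not called related does not appear in this table at all.

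**Working it through.** The plan gives no expected SAE rate, so there is no harms figure to reproduce. The nearest figure is in Section 3, Sample size, which claims 80% power for 0.36 vs 0.20 on a binary outcome such as hospitalization, with 98 per arm and a one-sided 0.05 test. It reproduces: power is 0.806 and the required size is 97 per arm. That proportion of 0.36 is used below as the upper end of the assumed risk.

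**Step 1. What the filter does when the arms are truly equal.**

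Inputs: arm sizes 156 and 125 (Section 7). Assumed, because the documents give neither: an equal six-month SAE risk *p* of 10%, 20% or 36%; a share *s* of intervention SAEs called related of 2% or 10%; and none in control.

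All-SAE count = n × p. Related-only count = n × p × s.

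| p | All SAEs, intervention vs control | Related only, s = 2% | Related only, s = 10% |
|---|---|---|---|
| 10% | 15.6 vs 12.5 | 0.3 vs 0 | 1.6 vs 0 |
| 20% | 31.2 vs 25.0 | 0.6 vs 0 | 3.1 vs 0 |
| 36% | 56.2 vs 45.0 | 1.1 vs 0 | 5.6 vs 0 |

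The all-SAE counts differ only by the arm-size ratio, 156/125 = 1.25. The related-only counts are small and fall on one side.

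**Step 2. What the filter hides.**

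Take an intervention risk of 20% and s = 10%. The related-only table shows 156 × 0.20 × 0.10 = 3.1 vs 0 whether the control risk is 10% (all SAEs 31.2 vs 12.5, a doubling) or 20% (31.2 vs 25.0, no difference). With no control events called related, the table carries no information on the control risk.

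**Step 3. Relaxing the zero.**

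Control events can be called related, for example after a blood draw. Let the control share be 2% and the intervention share 10%. At p = 10% the counts are 1.56 of 156 (1.0%) vs 12.5 × 0.02 = 0.25 of 125 (0.2%). At p = 36% they are 5.6 vs 0.9. With equal true risks, the ratio of related-event risks equals the ratio of the shares, here 0.10/0.02 = 5. It reflects how events were classified. Only equal shares would leave the comparison undistorted, and it would then rest on very few events.

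**Step 4. What the other by-arm outcomes cover.**

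- Source: the outcome definitions still allow self-report and/or record review, but Section 7 says records on utilization are not collected. The data are in effect self-reported.
- Missed visits: Section 6, Missing data, does not impute them. At the 20% attrition planned for in Section 3, about 156 × 0.20 = 31 and 125 × 0.20 = 25 participants would have no six-month report.
- Deaths: a participant who died cannot self-report. Reasons for loss in the CONSORT diagram may reveal some deaths, but the plan does not name death as an item.
- Serious events without hospital or urgent care are not captured.

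**Step 5. The time window.**

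The by-arm SAE sentence states none. Over full planned follow-up, before losses, exposure is 156 × 1.0 = 156 vs 125 × 0.5 = 62.5 person-years, a ratio of 2.5. Over months 0 to 6 it is 78 vs 62.5, a ratio of 1.25, which matches the arm sizes. If risk were constant at 10% per six months, the proportion with an SAE over 12 months would be 1 − 0.9² = 19%. Counting all follow-up would then show 29.6 of 156 (19%) vs 12.5 of 125 (10%) with no true difference in rate. Removing the relatedness filter without fixing the window would replace one distortion with another.

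**The case against.** The strongest defence is that the plan does not offer this table as a safety comparison, since it rules out formal analysis, and that two other outcomes do the comparing. Hospitalization and acute care use are reported by arm with no relatedness filter, are to be analysed with models like those for the primary outcome, and carry 95% confidence intervals and p-values. They can show harm or benefit and would capture much of what an SAE table contains. This stands. A reader might infer that the trial will have no informative safety comparison, or that any real excess or reduction in serious events will go unseen. The documents do not support either reading. The weakness is confined to the SAE table and to the gaps in Step 4.

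Four further points have weight:

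- The condition is relatedness to the study, not to the intervention, so procedure-related events in controls qualify. The control column need not be exactly zero, but Step 3 shows that the imbalance remains unless the shares are equal.
- A reader might take it as stated that unblinded staff judge relatedness. The plan says only that SAE information goes to the principal investigators. Knowledge of arm is a reasonable inference, not a documented fact.
- A reader might assume that an all-SAE table would be unbiased. It might not be. Controls have two assessments. Intervention participants also have two counselling sessions, four classes and weekly food contact, and no schedule of SAE enquiry is given, so ascertainment may favour detection in the intervention arm. An all-SAE table still avoids the causal judgement and keeps the randomised groups.
- The plan provides for SAE collection but does not show that unrelated SAEs were systematically sought in both arms. The new table can be only as complete as what was collected.

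**Conclusion.** The point holds as a defect in planned reporting. The only by-arm harms report is restricted in a way that would yield few events, mostly in the intervention arm, whatever the truth. Under the stated assumptions it would show about 0.3 to 5.6 events vs 0 where the unfiltered counts are 15.6 vs 12.5 up to 56.2 vs 45.0. The direction does not depend on the exact figures, only on intervention events being more likely than control events to be called related. That is itself an inference from the design.

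The reading that safety evidence in this trial is altogether uninformative goes too far, because hospitalization and acute care use are compared by arm without the filter. They compensate in part and do not replace a table of all SAEs and deaths. No efficacy estimate is affected.

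**What to change.** Replace the by-arm sentence in Section 6, Harms, with a commitment to:

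- report all SAEs and all deaths collected, by arm, regardless of relatedness;
- count them over the common baseline-to-six-month window, set by date because visits may be up to two months late;
- use all randomised participants as denominators, 156 and 125;
- show study-related SAEs as a sub-row, stating who judged relatedness, by what criteria, and whether they knew the arm;
- list intervention-arm events in months 6 to 12 separately, with no control comparison.

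Add a note that intervention participants had more staff contact, so ascertainment may differ by arm. In Outcome definitions, align the data source for utilization with Section 7.

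The cost is one sentence and one descriptive table, with no new test and no change to the primary analysis. The plan already provides for SAE collection. Six-month field work was due to finish in February 2025, so any gaps in collection may not be recoverable and should be stated beside the table.
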